5.3 Other Outcomes of Interest

Additional laboratory outcomes for a subset of participants only in participating centres:

- Linezolid plasma concentrations at day 4 or 5
- Minimal inhibitory concentration (MIC) of linezolid for the respective *S. aureus* strain

5.4 Safety Outcomes

Safety outcomes encompass any serious adverse events (SAE) and serious adverse reactions (SAR) until day 90 as well as adverse events of special interest. Definitions can be found in chapter 10.1.1 *Definition and assessment of (serious) adverse events and other safety related events*.

Adverse events of special interest

(details on how they are assessed is provided in chapter 9.2.4.1 *Adverse events*:

- Clinical signs of serotonin toxicity until day 7
- Laboratory signs of myelosuppression until day 7
- Hyperlactatemia until day 7
- Acute kidney injury
- *C. difficile*-associated diarrhoea within 90 days

Further information on safety outcomes (mortality, SAR, AEs leading to discontinuation of trial intervention) can be found in chapters 5.1 *Primary Outcome* and 5.2 *Secondary Outcomes*.

6. STUDY DESIGN

6.1 General study design and justification of design

LIPS is a pragmatic, multicentre, 1:1 randomised, parallel-group, placebo-controlled, superiority trial with blinded participants, physicians, and outcome assessors in the acute-care hospital setting (see Figure 1).

[figure not shown]

Figure 1: Schematic overview of the trial

The LIPS trial was designed with the involvement of four patient representatives to make sure that the assessed outcomes are patient relevant and that the burden due to the trial remains minimal for the participants. We have chosen a pragmatic trial mainly following routine care (i.e. the majority of outcomes are collected during routine care and the additional follow-up consists only of one phone call at day 90 and a quality-of-life questionnaire at day 90). However, as the outcomes can be influenced by expectations from participants (i.e. level of function) as well as the treating physicians (i.e. hospital length of stay) we have chosen a blinded study design to eliminate this source of bias.

6.2 Patient and Public Involvement

The following Patient and Public Involvement (PPI) has been and will be conducted to ensure that the trial is highly relevant to patients. We have been collaborating with four PPI representatives (two patient representatives who had complicated *S. aureus* bacteraemias as well as two patient experts) since the preparation of the funding application. These PPI representatives have agreed to lend their expertise for the duration of the trial up to the dissemination of the trial results. Ahead of every meeting, the PPI representatives are briefed on the current stage of the trial and the purpose of the meeting in layman's terms. Before the finalisation of the first protocol and patient informed consent draft, we conducted 3 focus group discussions with the four PPI representatives (2-4 hours/meeting).

6.2.1 PPI activities before receiving approval from authorities

PPI contribution	Outcome

 - Advised on the patient relevance of the proposed outcomes. - Informed the researchers about important aspects not covered by the proposed outcomes. - Discussed what the primary outcome should be and help with the exact definition. 	
 - Trial outcomes that are relevant to patients were chosen and ranked in order of importance (DOOR outcome). - PPI representatives advised to include a patient-reported outcome measure on quality of life at day 90.

 - Reviewed the eligibility criteria with a focus on inclusivity and making the trial results generalizable. 	
 - Broad inclusion criteria were chosen as recommended by the PPI representatives. - Exclusion criteria focus on safety aspects.

 - Provided feedback on how understandable the provided lay summary was. 	
 - Parts of lay summary were flagged as needing further explanation or simplifications and edited accordingly.

 - Advised on the chosen time points and if the study visits are useful and patient friendly. 	
 - Outcomes may also be collected by asking the participant's relatives or general practitioner. - Burden for participants with the proposed trial

 - Assessed burden for patients and identified ways to decrease burden, dropout rates and incomplete data selection. 	design was deemed very low.

 - Defined the further study phases during which PPI is critical and what form such involvement should take (guided by SCTO template). 	
 - PPI activities during and after trial conduct were planned (see chapter 6.2.2 PPI activities after receiving approval from authorities).

 - Provided feedback on draft patient information and informed consent form (ICF) in German. - Some PPI representatives will also assess patient information in other languages 	
 - ICF is concise and comprehensible, giving enough information without frightening patients regarding their diagnosis. - Patient-relevant information on background of the underlying disease, study procedures, risks and adverse events in layman's terms are included.

6.2.2 PPI activities after receiving approval from authorities

Planned PPI contribution	Objective

 - Advise on how to approach patients and relatives to inform them about study participation. 	
 - Incorporating PPI feedback into trainings of study sites on how to approach patients and relatives in a sensitive manner.

 - Participation in DSMB during prespecified interim analyses 	
 - Including the patient perspective when serious adverse are assessed in the interim analysis.

 - Discussing which of the results/effects are patient relevant and how to best visualise the data. 	
 - We will report all outcomes independent of the assessed effect. The objective of this exchange is to receive feedback which effects are most relevant for patients and how data should be visualised so that they can be understood easily

 - Advise on which form the results should be communicated. 	
 - Assuring that the study results are disseminated to a wide audience.

 - Support the communication of results in lay language. 	
 - Ascertaining that the study results can be communicated to participating patients and the general public.

 - Discussing the impact and the next steps with the researchers. 	
 - Making sure that appropriate action is taken based on the study results taking into consideration the patient perspective.

 - Evaluating the PPI involvement 	
 - Learning how best to involve PPI in future collaborative research projects

6.3 Methods of minimising bias

6.3.1 Randomisation

Participants will be allocated 1:1 to either linezolid or placebo for 5 days using block randomisation with varying random block sizes of 2 or 4 implemented in the data capture system REDCap®. For more details see chapter 7.3 *Assignment to study groups*.

6.3.2 Blinding procedures

The treatment allocation will not be revealed to any study staff or participants (i.e., physicians, study nurses, participants, outcome assessors). Only the unique randomization number will be visible for blinded personnel. The randomisation list will only be accessible to designated staff from Spital-Pharmazie Basel for manufacturing,

labelling and blinding the study medication, and the statistician who will prepare the randomisation list and upload it in REDCap®. The study medication will be packaged and dispensed by Spital-Pharmazie Basel to ensure that all participants, treating physicians, clinical investigators and study nurses involved in the study (including outcome assessors) will remain blinded to treatment allocation throughout the study.

6.3.3 Other methods of minimising bias

Not applicable.

6.4 Unblinding Procedures (Code break)

The study medication (10 tablets per container) with a unique randomisation number will be distributed to the study centres. For each unique randomisation number, the study centre will receive a sealed opaque envelope with the information if the container contains linezolid or placebo. The treating physician will only be allowed to open an envelope if safety concerns require knowing a participant's allocated intervention. All unblinding procedures must be entered within the eCRF. The envelopes will be checked during monitoring visits and after the completion of the study.

7. STUDY POPULATION

7.1 Eligibility criteria

Inclusion criteria:

- *S. aureus* grown from at least one blood culture
- Hospitalised at a participating centre
- ≥ 18 years old
- Written informed consent or fulfilling criteria for an emergency exception from informed consent requirements

Exclusion criteria:

- Administration of the initial drug treatment not feasible within 72 hours since the collection of the first positive blood culture with *S. aureus*
- Documented history of positive blood cultures for *S. aureus* occurring between 72 hours and 180 days prior to the eligibility assessment
- Necrotising fasciitis
- Currently receiving linezolid or clindamycin
- Use of any monoamine oxidase A or B inhibitor within the last two weeks
- Known hypersensitivity to linezolid or any other ingredients of the study drugs
- Current severe thrombocytopenia (i.e. $<30 \times 10^9/l$)
- Oral application of study drug not possible (per mouth or per gastric tube)
- Currently breastfeeding
- Local treating team believes that death is imminent and inevitable
- Patient is receiving end of life care and antibiotic treatment is not considered appropriate
- Local treating team believes that participation in the study is not in the best interest of the patient
- Any indication that the patient is unwilling to participate in the study including an advance directive stating such unwillingness

General:

Patients taking serotonergic drugs such as selective serotonin reuptake inhibitors (SSRI) or tricyclic antidepressants are not generally excluded. See detailed information on risk assessment and precautions in chapter 8.6 *Trial specific preventive measures*.

Pregnant women will not be excluded from study participation per se, as linezolid is not formally contraindicated during pregnancy. Limited data exist on the treatment of pregnant women with linezolid, mainly from clinical trials in treating multidrug-resistant tuberculosis. In 31 pregnancies under linezolid exposure, none reported foetal toxicity.⁹⁵ In the event of pregnancy, the treating physician and the patient (or the patient's next of kin) will assess whether the potential benefits outweigh the potential risks to the foetus.

Linezolid has been shown to pass into breast milk and accordingly, breastfeeding should be discontinued prior to and throughout administration of linezolid.

Patients will be recruited during their hospitalisation at participating centres. Patients will be flagged as soon as *S. aureus* is detected in a blood culture. The time required from blood collection to the confirmation of *S. aureus*, typically ranging from 12 to 36 hours, will depend on factors such as the time to positivity and the method employed for *S. aureus* identification.¹⁰⁸ The results will be immediately reported to the study team according to each centre's infrastructure - either via an automated electronic alarm system or via verbal communication from the clinical microbiology laboratory. Infectious disease specialists, serving as the local principal investigators at all participating centres, are routinely involved in the care of patients with *S. aureus* bacteraemia. Their involvement is well established and recognized for its positive impact on patient outcomes.¹⁰⁹⁻¹¹² Patients with blood cultures positive for *S. aureus* will be immediately screened for eligibility using the inclusion and exclusion criteria by the local PI or delegated physician. Eligible patients will be approached by the local study team as soon as possible. They will be informed about the LIPS trial via verbal and written study explanation, which consists of a printed summary in lay language including details of the intervention and potentially associated benefits and risks. Each participant will receive a consent form offering sufficient details to enable them to make an informed decision about their participation. For patients unable to give informed consent due to severe illness or other circumstances, it must be checked if a statement of wishes formulated in a state of capacity is available. If no such statement is available, an appropriate substitute (i.e., a close relative or a physician not involved in the research project) may make decisions based on the presumed wishes and the best interests of the patient as recommended by Swissethics.¹¹³ Participants who were included after receiving consent from their next of kin or confirmation by an independent physician will be asked to provide retrospective consent as soon as their health status allow an informed decision. The randomisation and intervention will start immediately upon the receipt of a formal written consent. Participants will not receive any financial compensation for their participation. The participating centres will receive financial reimbursement for establishing the local trial infrastructure and workflow as well as a reimbursement per participant to compensate for the costs of the study staff and other resources.

The sponsor notifies the CEC and the CA of the first study participant, in accordance with Art. 23a ClinO. If the first participating person is not included in the trial within two years following the issuance of the last authorization, the trial is considered interrupted. The clinical trial may then not be commenced until an application for an extension of the time limit has been approved. The application for the extension is submitted to the CEC, and to CA as a substantial amendment.

7.3 Assignment to study groups

Participants will be allocated 1:1 to either linezolid for 5 days or placebo for 5 days. The randomisation will be stratified by centre and ICU status at time of enrolment and done using block randomisation with varying random block sizes of 2 or 4. The trial statistician will generate the randomisation list outside of the data capture system REDCap®. This list will then be uploaded into the data capture system. The goal is to randomise participants such that the groups are as balanced as possible with respect to study centre and ICU status at time of enrolment.

After informed consent has been obtained and all eligibility criteria have been reviewed and met, the local investigator (or designated staff) enters the minimal required data into REDCap® (i.e., participant ID, year of birth, if participant is on ICU). The allocation is done by REDCap® which will display a unique, randomisation number that remains the same throughout the study. Each randomisation number will correspond to a drug container which is labelled with the unique randomisation number.

7.4 Criteria for withdrawal / discontinuation of participants

Participants can withdraw from the study at any time without providing a reason. Participants who discontinue the intervention will still be encouraged to complete follow-up assessments. Reasonable effort should be made to

establish the reason for discontinuation while fully respecting the participant's rights so reasons may be analysed. In case of adverse events, the treating physician decides (if possible, together with participants or close relatives) whether the study drug must be discontinued. Outcomes of these participants will still be collected, and they remain in the intention-to-treat analysis as randomised.

Participants who were included after receiving consent from their next of kin or confirmation by an independent physician will be asked to provide retrospective consent as soon as their health status allow an informed decision. If the participant refuses to give this retrospective consent, we will not collect any further data. However, we will analyse the data that has been collected up to this timepoint, as excluding these data could bias the analysis.

8. STUDY INTERVENTION

8.1 Identity of Investigational Medicinal Products

8.1.1 Experimental Intervention

The IMP in this study is linezolid 600 mg tablets (Linezolid STADA®) as described in chapter 3.2 *Investigational Medicinal Product (treatment) and Indication*. The IMP will be administered orally from day 1 until day 5, twice daily.

8.1.2 Control Intervention (standard/routine/comparator treatment)

Participants in the control arm will be receiving oral placebo tablets. Procedures regarding route of administration, study treatment duration and treatment phases will be identical in the IMP- and the placebo-group (see chapter 8.1.1 *Experimental Intervention*).

8.1.3 Packaging, Labelling and Supply (re-supply)

Linezolid STADA® and placebo tablets will be provided as trial supplies to the study centres re-packaged in identical opaque containers by Spital-Pharmazie Basel. Each container will contain 10 tablets of either linezolid 600 mg or placebo. The containers will be labelled identically except for the unique randomisation number on each container. Spital-Pharmazie Basel will be responsible for the labelling, packaging, and shipping of the IMPs. Each centre will be supplied with a minimum number of containers at site initiation. The label contains the information required by the authorities.

The trial manager will monitor the recruitment progress of the individual study centres and will inform Spital-Pharmazie Basel if re-supply is needed. Spital-Pharmazie Basel will arrange for the shipment of the re-supply to the centres following instructions by the trial manager.

8.1.4 Storage Conditions

The IMP must be kept in a secure, limited access storage area under the recommended storage conditions (i.e. identical storage conditions apply as for linezolid tablets that are used in routine practice at the study centre).

8.2 Administration of experimental and control interventions

8.2.1 Experimental Intervention

One linezolid 600 mg tablet will be administered orally twice a day on 5 consecutive days (chapter 3.4 *Clinical Evidence to Date*). For hospitalised participants, the study drug will be distributed in the same manner as a participant's other oral medication. The local investigator or delegated staff will hand over the study drug to the nursing team who will distribute the study drug to the participant according to the instructions by the physician and according to the site-specific local procedures. In general, each dose/each tablet will be distributed separately to the participant and only just before intake. If, based on the treating team's assessment, a participant is unable to swallow the study medication, tablets may be crushed and resuspended for easier consumption or for administration via a nasogastric tube according to clinical routine and following site-specific SOPs.

In the unlikely event that participants are discharged home before day 5, they will receive the remaining study medication along with detailed instructions on how and when to take them at home.

8.2.2 Control Intervention

Dosing and administration of the placebo tablets are the same as for participants in the experimental intervention arm.

8.3 Dose modifications

Drug-related AEs leading to discontinuation of the drug are expected to be extremely rare when linezolid is used for 5 days. Discontinuation of IMP may occur in the situations listed in chapter 6.4 *Unblinding Procedures (Code*

break) and chapter 7.4 *Criteria for withdrawal / discontinuation of participants*. The study medication will be given twice a day for 5 days (in total 10 administrations) with approx. 12 hours interval between each administration. If maintaining a fixed 12-hour interval is challenging due to the start time (e.g. if subsequent doses would need to be administered in the middle of the night), the treating physician may adjust the first dosing interval according to standard practice. However, the interval should not be shortened or extended by more than 6 hours. Further dose modifications are not allowed.

8.4 Compliance with study intervention

The intake of the study medication will be documented for each tablet (date and time) either electronically in the participant's eCRF or directly on a separate leaflet (which will be later transferred to the eCRF). Any missed doses, along with the reasons for missing them, must also be documented. The participant will receive instructions for the correct storage and administration of IMP at the ward if discharge occurs before completion of the 5-day intervention phase.

8.5 Data Collection and Follow-up for withdrawn participants

Participants can discontinue the trial intervention at any time without providing a specific reason. Participants who wish to withdraw from the study will commonly receive further measurements as part of clinical routine. We will ask these participants if we are allowed to collect the corresponding routine clinical data and/or to contact them on day 90 to assess the primary outcome.

8.6 Trial specific preventive measures

Thrombocytopenia is a common adverse event of linezolid, but it is usually associated with treatment durations of 10 or more days. Given the lifespan of thrombocytes and the short intervention duration of five days in our study, we expect a low risk of linezolid-mediated thrombocytopenia. However, thrombocytopenia is also commonly seen in participants undergoing sepsis. If participants develop severe thrombocytopenia during the intervention, the local investigator should assess if this may be associated with the trial medication and decide on stopping or continuing the intervention for this participant.

Linezolid should not be used in patients taking any medicinal product which inhibits monoamine oxidases A or B (e.g. the antidepressant moclobemide or the Parkinson's medications rasagiline and safinamide) or within two weeks of taking any such medicinal product.

For participants taking serotonergic agents, the local investigator should evaluate if pausing the serotonergic medication for the duration of the trial is possible. If not, the local investigator (or delegate) should decide if the participant can be included ensuring that potential signs of serotonin toxicity are monitored for the duration of the study intervention phase, or if the patient should be excluded. On trial days 1-5, clinical observation for signs of serotonin toxicity is required for participants taking any of the following medications: serotonin re-uptake inhibitors, tricyclic antidepressants, serotonin 5-HT1 receptor agonists (triptans), directly and indirectly acting sympathomimetic agents (including the adrenergic bronchodilators, pseudoephedrine and phenylpropanolamine), vasopressive agents (e.g. epinephrine, norepinephrine), dopaminergic agents (e.g. dopamine, dobutamine), pethidine or buspirone.

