medication includes other serotonergic drugs such as selective serotonin reuptake inhibitors (SSRIs) or tricyclic antidepressants, can potentially experience an increase in serotonin activity. The clinical effects of serotonin excess range from mild serotonin-related side effects to severe serotonin toxicity.^{80 81} In the largest meta-analysis involving 2208 patients receiving linezolid and 5058 patients not receiving linezolid, the observed incidence of serotonin toxicity was 0.4% among patients taking linezolid in combination with a serotonergic agent (compared to 0.15% in those taking a serotonergic agent alone).⁸² Similarly, in a large cohort of 1135 patients, fewer than 0.5% experienced serotonin toxicity.⁸³ Assuming 20% of study participants are on serotonergic drugs, we would expect an additional 0-1 participants with serotonin toxicity in the linezolid arm compared to the placebo arm. In view of the low incidence of clinically relevant serotonin toxicity combined with the study design ensuring adequate monitoring of participants, patients on serotonergic agents are not excluded from study participation. A detailed list of such medications can be found in chapter 8.6 *Trial specific preventive measures*.

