9.3.9 Assessment of SIRS criteria (day 5 ± 1)

The components of the SIRS criteria (abnormal body temperature, mechanical ventilation, tachycardia, and abnormal leucocytes) are routinely assessed and documented during clinical management of the hospitalised participants. The vital parameters (body temperatures, respiratory rate, pulse) are usually measured at least once daily. Leukocytes are usually measured every 1-3 days. Tachypnoea is assessed when clinically indicated. Thus, these criteria will be collected from the hospital information system data.

9.3.10 Measurement of trough levels of linezolid in a subset of participants (day 4-5)

Participating centres will collect one 7.5 ml Monovette® Li-Heparin from participants between day 4 and 5 after randomisation for a representative linezolid trough measurement. Plasma sampling may be combined with the routine blood draw but should be timed immediately before the next linezolid dose.

Plasma should be isolated by centrifugation and frozen as soon as possible after blood draw, but at the latest within 6 hours. Samples will be stored at -80°C until shipment. Periodically, samples are shipped on dry ice to the University Hospital Basel where linezolid trough levels will be analysed by the diagnostic laboratory.

9.3.11 Assessment of adverse events of special interest (day 1-5, day 14 ±3, discharge day)

- Clinical signs of serotonin toxicity until day 7: Serotonin toxicity will be assessed during clinical routine. Participants will routinely be visited daily by the treating physician. Daily measurement of vital signs including blood pressure is part of the clinical routine. In case of clinical signs of serotonin toxicity, the Hunter criteria and diagnostic algorithm will be used (including spontaneous or inducible clonus, ocular clonus, tremor, hypertonia and hyperthermia, agitation or diaphoresis, hyperreflexia). In case of clinical signs of serotonin toxicity, the IMP administration will be halted. The local investigator will be involved to re-assess the clinical picture and to confirm or reject the observation. The local investigator will then decide if the participant can continue taking the IMP or needs to stop the intervention.

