10. SAFETY

10.1 Drug studies

During the entire duration of the study, all serious adverse events (SAEs) are collected, fully investigated and documented in source documents and case report forms (CRF). Predefined adverse events of special interest (AE) critical to the safety evaluation will be assessed as outlined in the study protocol. Study duration encompasses the time from when the participant signs the informed consent form until the last protocol-specific procedure has been completed, including a safety follow-up period.

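### Section 8.6 asks about pausing serotonergic medication for the whole trial, although study drug is given only on days 1–5

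*Protocol*

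**What the plan says.** Linezolid is a weak monoamine oxidase inhibitor, and patients on serotonergic drugs may still enter the trial. Synopsis and section 7.1 send the reader to one place for the safeguards: "See detailed information on risk assessment and precautions in chapter 8.6". Section 3.8 points to the same section for the list of drugs.

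Section 8.6 then sets out two steps. First, "the local investigator should evaluate if pausing the serotonergic medication for the duration of the trial is possible". Second, where it is not, the investigator decides between exclusion and inclusion with signs of serotonin toxicity "monitored for the duration of the study intervention phase". The sentence after that requires clinical observation on days 1 to 5 for participants taking any of the listed drugs.

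The dosing period is stated consistently: days 1 to 5 in section 8.1.1, ten administrations in section 8.3, and in section 8.4 the case "if discharge occurs before completion of the 5-day intervention phase". The end of participation is stated in section 10.1: "Study duration encompasses the time from when the participant signs the informed consent form until the last protocol-specific procedure has been completed", with safety follow-up included. The last scheduled contact is at day 90 ±7 (section 9.1). Serotonin toxicity is collected until day 7 (sections 5.4, 9.1 and 9.2.4.1).

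**The concern.** Pausing the serotonergic drug and monitoring for toxicity are alternatives for the same interaction, so one would expect them to cover the same period. They do not: the pause is tied to the trial, the monitoring to the intervention phase. No other section sets a period for the pause or says when the paused drug may be restarted.

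The pause question comes before the choice between inclusion with monitoring and exclusion, so its period matters. Stopping an antidepressant for five days may be acceptable where stopping it to day 90 is not. A site that applies the text literally could:

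- judge a feasible short pause to be infeasible, and then include the patient on both drugs;
- for the same reason, exclude the patient;
- pause the home medication and keep it paused long after the last dose of study drug.

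What is at stake is the care of individual participants and some avoidable exclusions, not the statistical comparison.

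**Working it through.** The main check sets the protocol's periods side by side.

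| Item | Period | Section |
|---|---|---|
| Pause of serotonergic drug | the trial | 8.6 |
| Monitoring if no pause | study intervention phase | 8.6 |
| Required clinical observation | days 1–5 | 8.6 |
| Study drug | days 1–5, 10 doses | 8.1.1, 8.3 |
| Intervention phase | 5 days | 8.4, 9.1 |
| Serotonin toxicity collected | until day 7 | 5.4, 9.1, 9.2.4.1 |
| Study duration for a participant | consent to last procedure, day 90 ±7 | 10.1, 9.1 |

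The pause is the only interaction measure not tied to dosing or to the first week.

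**Length of the two periods**

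- Doses: 2 per day × 5 days = 10, as section 8.3 states.
- First to last dose: 9 intervals × 12 h = 108 h = 4.5 days. With the first interval shifted by up to 6 h (section 8.3): 102–114 h, or 4.25–4.75 days.
- Literal pause, taking section 10.1's study duration: to day 90, range 90 − 7 = 83 to 90 + 7 = 97.
- Ratio: 90 / 5 = 18.

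**Who the instruction concerns.** Section 3.8 assumes 20% of participants take serotonergic drugs: 0.20 × 606 = 121.2 in the trial, 0.20 × 303 = 60.6 in the linezolid arm.

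**Bound on the co-exposure consequence.** Section 3.8 gives serotonin toxicity of 0.4% with linezolid plus a serotonergic agent and 0.15% with the serotonergic agent alone. If nobody pauses:

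60.6 × (0.0040 − 0.0015) = 60.6 × 0.0025 = 0.15 additional cases.

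This agrees with the protocol's own statement that "we would expect an additional 0-1 participants with serotonin toxicity in the linezolid arm compared to the placebo arm". The figure bounds co-exposure only. It does not measure avoidable exclusions or over-long withdrawal, and the protocol gives nothing from which either could be estimated.

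**The case against.** The strongest reply is that section 8.6 supplies the right period itself. Its first paragraph mentions the five-day intervention, the sentence after the pause refers to the intervention phase, and the next one to days 1 to 5. The reason for pausing is linezolid, which stops on day 5. Infectious disease specialists will probably read it that way. This stands as to intent, and is why the point is minor. It does not make the written period correct in an instruction to be used at approximately 12 centres.

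The protocol also orders no pause. It asks for an evaluation, states that patients on serotonergic drugs are not generally excluded, and accepts co-exposure under observation; section 9.3.11 adds: "In case of clinical signs of serotonin toxicity, the IMP administration will be halted". This stands too, and rules out any claim of a large safety risk.

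Four stronger readings are tempting, and the documents do not support them.

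- *The protocol requires a 90-day withdrawal.* It does not. Day 90 is an inference: section 10.1 defines study duration in a safety-reporting context and does not define the phrase used in section 8.6.
- *Section 6.2 shows that the phrase means the whole trial.* It does speak of involvement "for the duration of the trial up to the dissemination of the trial results", but this describes how long patient representatives contribute and says nothing about a participant's medication.
- *The pause should plainly end at the last dose.* The protocol collects serotonin toxicity until day 7 and gives no washout interval, so the restart time is a clinical decision for the sponsor.
- *The wording biases the comparison or costs power.* The decision is made for blinded participants at or around entry, and nothing in the protocol links it to the assigned arm.

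**Conclusion.** The point holds as a minor correction. Section 8.6 gives the wrong period in an operative safety instruction: the pause is tied to the trial, while study drug is given on days 1–5 and the alternative safeguard covers only the intervention phase. The mismatch is certain from the text. That the five-day phase was meant is probable. That a site would act on the longer period is possible, and its frequency is unknown.

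On size, the literal period is about day 90 against five days of dosing, assuming section 10.1's study duration applies. Co-exposure adds at most about 0.15 toxicity cases under section 3.8's assumptions (20% on serotonergic drugs; 0.4% against 0.15%). The more practical consequences, an avoidable exclusion or a needlessly long withdrawal, cannot be quantified. No effect on bias, power or outcomes follows.

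**What to change.** In section 8.6, replace the period in the pause sentence with *for the duration of the study intervention phase (days 1–5)*, matching the sentence that follows it. Add that the sponsor sets the earliest restart after the last dose, consistent with the protocol's serotonin-toxicity window (until day 7), with resumption then at the treating physician's discretion.

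The restart should be counted from the actual last dose. Section 9.3.5 allows the first dose at any hour, and ten doses span about 108 h, so a late start on day 1 can put the tenth dose on day 6.

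The cost is one phrase and one short sentence in the next amendment, plus the sponsor's decision on the restart time. Design, sample size and analysis are unchanged.
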